- Informed consentand study assessments completed electronically. Informed consent for the study will be obtained through a phone call with study staff and electronically through a Research Electronic Data Capture (REDCap) survey sent via e-mail. All study assessments will be obtained through REDCap surveys sent via e-mail.
- Appropriate COVID-19 screening procedures and personal protective equipment (PPE) will be
 utilized for all acupuncture treatment visits. We will screen participants for COVID-19 by phone 1-2
 days before each scheduled acupuncture treatment visit and also the day of the clinic visit. If a
 patient screens positive for COVID-19, study visits will be postponed for the appropriate amount of
 time per current guidance, and we will follow the current clinic site process for COVID-19 positive
 screens, as defined by the medical group. This study will also align with the HealthPartners
 Neuroscience Center policies regarding PPE for in-person visits. This will be done to ensure the
 safety of patients and study staff.
- Finally, this study will align with HealthPartners Neuroscience Center's COVID-19 policies and procedures.

Protocol Amendment Version 4: Summary of changes to the protocol due to the COVID-19 Pandemic

• Addition of COVID-19 Questions. The addition of questions related to COVID-19 will be done to potentially explore whether acupuncture has an effect on post-COVID-19 symptoms. The questions below will be asked at 2 time points: at the beginning of first acupuncture appointment and at the 4-week post-treatment visit (4 weeks after the last acupuncture treatment). They will be collected electronically via REDCap. As an exploratory analysis, patients who report post-COVID-19 symptoms will be identified using the additional COVID-19 set of questions. Types and severity of post-COVID-19 symptoms present within the group will be described. The t-test or non-parametric equivalent will be used to determine whether acupuncture had an effect on post-COVID symptoms. The protocol has been updated to reflect the changes and the questions are listed below.

Questions:

- 1) Have you previously received a positive test for COVID-19? (yes/no)
- 2) Were you exposed to someone with a positive test, subsequently developed symptoms, but did not get a COVID-19 test? (yes/no)
- 3) Are you currently experiencing any of the following post-COVID-19 symptoms?

(Drop down list with most common symptoms, select all that apply)

- a. Fatigue

1.1 SYNOPSIS

Title: Acupuncture Treatment for Chronic Post-traumatic Headache in

Individuals with Mild Traumatic Brain Injury.

IRB Number: A19-094

Study Description: The purpose of the study is to determine the effect of a low vs. high

dose of acupuncture treatment in individuals with chronic post-traumatic headache (CPTH). A total of 40 people with mild traumatic brain injury (mTBI) suffering from CPTH will be enrolled in this study to

receive acupuncture treatment for 5 weeks. Participants will be randomized into two groups: 1) Low Acupuncture group (5 treatments) and 2) High Acupuncture group (10 treatments). We hypothesize that both treatment groups will have decreased headaches, but that 10 treatments will greater alleviate headaches when compared to 5

treatments.

Specific Aims: Specific Aim 1: To determine the effect of a low versus high dose

acupuncture treatment on number of headache days for individuals

suffering from CPTH.

Specific Aim 2: To determine the safety and tolerability of acupuncture

on CPTH in individuals with mTBI.

Specific Aim 3: To explore the effects of acupuncture on sleep, quality of life (QOL), headache outcomes, and medications in individuals

with mTBI who suffer from CPTH.

Endpoints: Primary Endpoint: Number of headache days over 4 weeks

Secondary Endpoints: 1) Adverse or Serious Adverse Events and 2)

Completion of treatment durations and sessions

Exploratory Endpoints: 1) Sleep, 2) Quality of life, 3) Headache

Outcomes, and 4) Medications

Study Population: 40 individuals aged 18-70 with a diagnosis of mTBI suffering from CPTH

will be recruited for this study.

Description of

Sites/Facilities Enrolling

Participants:

Participants will be enrolled at HealthPartners Neuroscience Center, and will be treated at the Neuroscience Center, HealthPartners Clinic

St. Paul Como, or Healing Response Acupuncture & Functional

Neurology.

Description of Study
Intervention/Experimental

intervention, Experimenta

Manipulation:

Acupuncture treatment will be administered by a licensed

acupuncturist for a duration of 5 weeks. One treatment group will receive 5 treatments and the other will receive 10 treatments.

Study Duration: The duration of this study is 2 years.

Participant Duration: Participants should complete all study-related tasks within 176 days

(approximately 6 months).

1.2 SCHEMA

Pre-screen potential participants by inclusion and Pre-screening exclusion criteria. Phone Call Schedule Pre-treatment Visit. **Pre-treatment Visit** Conduct informed consent process. Perform baseline assessments: Visit 1 Pittsburgh Sleep Quality Index (PSQI) (Day 1) Traumatic Brain Injury-Quality of Life (TBI-QOL) short forms Medication Review Randomize N = 36Arm 1 Arm 2 N = 18N = 18Study intervention (Low Dose) Study intervention (High Dose) Acupuncture treatment Acupuncture treatment Visits 2-6 [Arm 1] 1x/week for 5 weeks (5 total) 2x/week for 5 weeks (10 total) Visits 2-11 [Arm 2] Completed Headache Diary Completed Headache Diary (Days 29 + 14 to Adverse Events Reporting Adverse Events Reporting 64 + 14)**Medication Review Medication Review** Treatment Adherence Treatment Adherence 4-week Post-treatment Visit Perform assessments: Completed Headache Diary Visit 7 [Arm 1] Adverse Events Reporting Visit 12 [Arm 2] (Day 71-106 + 7) Medication Review **PSOI** TBI-QOL short forms 12-week Post-treatment Visit Perform final assessments: Completed Headache Diary Visit 8 [Arm 1] Adverse Events Reporting Visit 13 [Arm 2] Medication Review (Day 127-169 + 7) TBI-QOL short forms

1.3 SCHEDULE OF ACTIVITIES

	Pre-screening Phone Call	Pre-treatment Visit	Study Intervention	4-week Post- treatment Visit	12-week Post- treatment Visit
Arm 1: 5 Treatments	Visit 0	Visit 1	Visit 2-6	Visit 7	Visit 8
Arm 2: 10 Treatments	VISIL U	VISIL 1	Visit 2-11	Visit 12	Visit 13
Review Eligibility	Х				
Informed Consent		Х			
Demographics		Х			
Randomization		Х			
Medication Review		Х	х	Х	Х
Completed Headache Diary			Х	Х	Х
Pittsburgh Sleep Quality Index (PSQI)		х		Х	Х
Traumatic Brain Injury-Quality of Life (TBI-QOL) short forms		Х		Х	Х
Adverse Events (AE) Reporting			Х	Х	Х
Treatment Adherence			Х		

VISIT SCHEUDULE DESCRIPTION

All in-person visits will take place at: HealthPartners Neuroscience Center, [name], or HealthPartners Clinic St. Paul Como, [name], or Healing Response Acupuncture & Functional Neurology, [name].

1. Pre-screening Phone Call

- Duration: Approximately 30 minutes
- Research staff will:
 - o Provide potential participants information about the study and ask whether they are interested in participating.
 - o Determine whether they meet the inclusion/exclusion criteria for the study.
 - Ask participants for permission to communicate through e-mail for the study (e.g. send them study documents and surveys to complete).

- o Assist participants with setting up an e-mail account, if they do not have one.
- Schedule Pre-treatment Visit if the person is eligible for the study and e-mail the person the Informed Consent, Health Insurance Portability and Accountability Act (HIPAA), and HealthPartners non-discrimination forms.

2. Pre-treatment Visit

- Duration: Approximately 1 hour via phone
- Research staff will:
 - o Review the Informed Consent and HIPAA documents with potential participants.
 - Answer any questions of potential participants and ensure they understand the expectations of the study.
 - Ask participants to electronically sign the Informed Consent and HIPAA documents via REDCap and provide them electronic copies for their records.
 - Complete the Demographics and Medication Reviewshort forms in the relevant electronic case report forms (eCRFs) in Research Electronic Data Capture (REDCap), a secure web-based system.
 - © E-mail the Pittsburgh Sleep Quality Index (PSQI) and Traumatic Brain Injury-Quality of Life (TBI-QOL) surveys to the patient for completion. Ask patients to complete the surveys prior to their first acupuncture visit. During the reminder call for the acupuncture visit, patients will be reminded to complete the surveys if they have not yet completed them.
 - Provide participants instructions regarding the Headache Diary REDCap survey (example script below):
 - "You will receive a Headache Diary survey via e-mail once a week for the next 4 weeks. Each survey will ask questions about your headaches over the last week. What is most important for you to remember is the number of headaches you had. The rest of the information is also helpful."
 - 2. Provide participants a paper diary and ask them to use it to keep track of their headaches during the week. Instruct participants that they should use it to fill out the weekly e-mail survey.
 - 3. Show participants an example of the REDCap survey.

3. Study Intervention

- Duration: Each visit approximately 1 hour
- A study acupuncturist will:
 - Complete the Adverse Events (AE) Reporting, Medication Review, and Treatment Adherence in the relevant eCRFs in REDCap.
 - o Perform the acupuncture treatment.
- Only at the LAST acupuncture visit, a study acupuncturist will:
 - Provide participants instructions regarding the Headache Diary REDCap survey (example script below):
 - "Like you experienced before, you will receive a Headache Diary survey via e-mail once a week for the next 4 weeks. Each survey will ask questions about your headaches over the last week. What is most important for you to remember is the number of headaches you had. The rest of the information is also helpful."

2. Provide participants a paper diary and ask them to use it to keep track of their headaches during the week. Instruct participants that they should use it to fill out the weekly e-mail survey.

3. Show participants an example of the REDCap survey.

4. 4-week Post-treatment Visit

- Duration: Approximately 30 minutes via phone
- Research staff will:
 - Complete the AE Reporting and Medication Review forms in the relevant eCRFs in REDCap.
 - o E-mail the PSQI and TBI-QOL surveys to the patient for completion. Ask patients to complete the surveys within one week. Five days after the visit, patients will receive a reminder call if they have not yet completed the surveys.
 - Provide participants instructions regarding the Headache Diary REDCap survey (example script below):
 - "Like you experienced before, you will receive a Headache Diary survey via e-mail once a week for the next 4 weeks. Each survey will ask questions about your headaches over the last week. What is most important for you to remember is the number of headaches you had. The rest of the information is also helpful."
 - 2. Provide participants a paper diary and ask them to use it to keep track of their headaches during the week. Instruct participants that they should use it to fill out the weekly e-mail survey.
 - 3. Show participants an example of the REDCap survey.

5. 12-week Post-treatment Visit

- Duration: Approximately 30 minutes via phone
- Research staff will:
 - Complete the AE Reporting and Medication Review forms in the relevant eCRFs in REDCap.
 - E-mail the PSQI and TBI-QOL surveys to the patient for completion. Ask patients to complete the surveys within one week. Five days after the visit, patients will receive a reminder call if they have not yet completed the surveys.

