2 INTRODUCTION

2.1 BACKGROUND & STUDY RATIONALE

Chronic post-traumatic headache (CPTH) after a mild traumatic brain injury (mTBI) is extremely debilitating, dramatically impacts function and quality of life, and is the most frequent type of chronic pain reported after injury.¹ It has been estimated that approximately 17.1 million Americans suffer a traumatic brain injury (TBI) each year,² with CPTH estimated to occur in 57.8% of these individuals.³ CPTH presents as: 1) tension-like (mild-moderate dull pain), 2) migraine headache (moderate-severe throbbing pain), or 3) combined tension-like and migraine headache.¹ On average, the number of reported headache days each month for individuals suffering from CPTH is 26,⁴ which is almost daily. Individuals suffering from CPTH are more likely to have post-traumatic stress disorder, cognitive symptoms, and somatic symptoms.⁴ They are also more likely to perceive difficulties in their physical and social function.⁴ Consequently, it is not surprising that CPTH is extremely agonizing and frustrating for individuals with mTBI.

There are currently no FDA approved pharmacological treatments specifically for CPTH and the long-term effects of pharmacologic treatments on recovery after TBI are unclear. Thus, individuals are typically prescribed medications that target the particular type of headache (e.g. triptan for a migraine headache). Non-narcotic analgesics, nonsteroidal anti-inflammatory drugs (NSAIDs), and triptans are often prescribed for headache and migraine treatment and have been recommended to be coupled with non-pharmacological treatments, such as physical therapy, biofeedback, and relaxation training. However, because the long-term effects of pharmacologic treatments on recovery after TBI are unclear, non-pharmacologic or behavioral treatments for CPTH are very appealing.

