8 STUDY ASSESSMENTS AND PROCEDURES

8.1 ENDPOINT AND OTHER NON-SAFETY ASSESSMENTS

Demographics: Demographic information will be collected, including: gender, age, race, ethnicity, language, height, weight, marital status, employment status, date of TBI, date of CPTH diagnosis, and email address for Headache Diary surveys (discussed below).

Medication Review: Medication data will be used for exploratory purposes for Specific Aim 3.

Headache Diary: Participants will be sent an e-mail REDCap survey to complete and asked to record headache information for three 4-week time periods. During each 4-week period, they will receive the e-mail once per week. They will be provided paper headache diaries (Appendix 1-3) to keep track of their headaches and will be asked to complete each e-mail survey they receive. The headache diary survey will include: how many headaches occurred each week during the 4-week period, duration, pain intensity (0-10 scale), type (e.g. tension), and name of medication taken and dosage (if applicable). The outcome measure for Specific Aim 1 is number of headache days over 4 weeks; other variables will be exploratory.

Treatment Adherence: The participant's treatment adherence will be measured to determine tolerability of acupuncture. We will record the number of attended acupuncture sessions. We will also record participants' ability to maintain the acupuncture duration of 30 minutes per session.

Sleep: Participants will be asked to complete the Pittsburgh Sleep Quality Index (PSQI), which contains questions about one's usual sleep habits during the past month.

Quality of Life: Participants will be asked to complete the TBI-QOL short forms. The TBI-QOL includes the following domains: ability to participate in social roles and activities, anger, anxiety, attention-concentration, cognition-general concerns, communication, depression, emotional behavior dyscontrol, executive function, fatigue, grief-loss, headache pain, independence, learning-memory, mobility, pain interference, positive affect and well-being, resilience, satisfaction with social roles and activities, self-esteem, stigma, and upper extremity.

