8.3.4 TIME PERIOD AND FREQUENCY FOR EVENT ASSESSMENT AND FOLLOW-UP

The occurrence of an AE or SAE may come to the attention of study personnel during study visits and interviews of a study participant.

All AEs, not otherwise precluded per the protocol, will be captured on the appropriate eCRF. Information to be collected includes event description, time of onset, clinician's assessment of severity, relationship to study procedures (assessed only by those with the training and authority to make a diagnosis), and time of resolution/stabilization of the event. All AEs occurring while on study will be documented appropriately regardless of relationship. All AEs will be followed to adequate resolution.

Any medical or psychiatric condition that is present at the time that the participant is screened will be considered as baseline and not reported as an AE. However, if the study participant's condition deteriorates at any time during the study, it will be recorded as an AE.

Changes in the severity of an AE will be documented to allow an assessment of the duration of the event at each level of severity to be performed. Documentation of onset and duration of each episode will be maintained for AEs characterized as intermittent.

Study staff will record events with start dates occurring any time after the first acupuncture treatment session until the 12-week post-treatment visit. At each acupuncture treatment visit (after the 1st) and the 4-week and 12-week post-treatment visits, study staff will inquire about the occurrence of AE/SAEs since the last visit. All reported events will be monitored until the 12-week post-treatment visit. Any reported event that is definitely or probably related to the intervention will be followed until resolution or stabilization.

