9.4.5 BASELINE DESCRIPTIVE STATISTICS

Baseline variables will be compared between groups to ensure randomization achieved balanced treatment assignments. This will include demographics (e.g. gender, age, race) and medical history (e.g. length of stay in hospital after injury, discharge destination). All such variables are listed in section 8.1 of this document. Variables will be summarized using descriptive statistics (e.g. mean and SD, or frequency and proportion) and compared inferentially. Continuous variables will be compared using two-sample t-tests or Wilcoxon rank tests and discrete variables will be compared using chi-square tests for independence or Fisher's exact tests.

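### No medical-history or symptom record is taken before treatment, so the baseline rule for adverse events in 8.3.4 rests on recall for dizziness, nausea, disturbed vision, tinnitus and imbalance

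*Combined protocol and SAP*

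**What the plan says.** Section 8.3.4 sets the baseline rule, under which existing conditions are not AEs: "Any medical or psychiatric condition that is present at the time that the participant is screened will be considered as baseline and not reported". The next sentence covers worsening: if the participant's "condition deteriorates at any time during the study, it will be recorded as an AE". A third sentence sets the window: "Study staff will record events with start dates occurring any time after the first acupuncture treatment session until the 12-week post-treatment visit". No record is named against which presence or deterioration is to be judged.

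For the pre-treatment visit, section 1.3 (item 2) tells staff: "Complete the Demographics and Medication Reviewshort forms in the relevant electronic case report forms (eCRFs". The same item has participants complete PSQI and TBI-QOL before the first acupuncture visit and starts a four-week headache diary. The Schedule of Activities has no row for medical history or symptoms.

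The demographics list in 8.1 ends with "date of TBI, date of CPTH diagnosis, and email address for Headache Diary surveys (discussed below" and holds no history or symptom item. Yet 9.4.5 says that the baseline comparison will include "medical history (e.g. length of stay in hospital after injury, discharge destination). All such variables are listed in section 8.1 of this document".

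**The concern.** Both halves of the 8.3.4 rule compare a report made during the study with the participant's earlier state. Several effects listed in 2.2.1 are symptoms that a person with post-traumatic headache may already have. Section 2.1 says so in general terms: "Individuals suffering from CPTH are more likely to have post-traumatic stress disorder, cognitive symptoms, and somatic symptoms". If a participant mentions dizziness at a treatment session, someone must decide whether it is new, unchanged or worse. With no earlier record, the decision rests on memory.

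AEs are one of the two secondary endpoints and the core of Aim 2. Section 9.4.3 reports the proportion of each arm with at least one AE or SAE, with an odds ratio and 95% confidence interval. An existing symptom logged as new raises that proportion; a true worsening taken for an old complaint lowers it. Personnel are unblinded (6.3), the treating acupuncturists complete the AE form (1.3, item 3), and there is no data safety monitoring board (10.1.6). A written baseline would therefore be especially useful here.

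**Working it through.** The plan gives no figure on this point to reproduce. The check sets the sections side by side; the arithmetic in step 5 is illustration only.

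**1. What is recorded before the first needle.** Demographics and medication review (1.3, 8.1); PSQI and TBI-QOL (1.3); the four-week headache diary with count, duration, intensity, type and medication (1.3, 8.1); and the COVID-19 questions at the first acupuncture appointment (version 4 amendment summary; their use is confirmed in 9.4.9).

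**2. Coverage.** Eleven effects in 2.2.1 are symptoms that this population might already have:

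| Effect in 2.2.1 | Pre-treatment measure described |
|---|---|
| Headache | Diary; TBI-QOL headache pain |
| Fatigue | TBI-QOL; COVID-19 item |
| Anxiety | TBI-QOL |
| Depressive mood | TBI-QOL depression |
| Sleep disturbance | PSQI; COVID-19 item |
| Poor concentration | TBI-QOL attention-concentration; COVID-19 item |
| Dizziness | None |
| Nausea | None |
| Disturbed vision | None |
| Tinnitus | None |
| Imbalance | None |

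Six are measured and five are not. The COVID-19 question has a free-text option, but it asks only about post-COVID symptoms.

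**3. Link to AE assessment.** Sections 3, 8.1 and 9.4.9 assign these measures to the primary or exploratory aims. Sections 8.2 and 8.3 mention none of them. PSQI and TBI-QOL are repeated only at the 4-week and 12-week post-treatment visits, so there is no concurrent score when a symptom is reported during the treatment weeks.

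**4. Timing.** Baseline is fixed at screening. The schema puts the pre-treatment visit on Day 1 and the first session on Day 29 or later, at least 29 − 1 = 28 days on. The AE window opens after the first session. A symptom that begins in between is neither baseline nor an AE.

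**5. Size.** The endpoint in 9.4.3 is not limited to related events. With 18 per arm (4.1), one misclassified participant moves the proportion by 1/18 = 5.6 percentage points; with 20 per arm (40 enrolled, synopsis), by 1/20 = 5.0 points.

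The documents give no misclassification rate. Assume a chance q, at each scheduled AE enquiry, that an existing symptom is logged as new. Section 8.3.4 schedules enquiries at each session after the first and at both post-treatment visits: 4 + 2 = 6 in the 5-session arm and 9 + 2 = 11 in the 10-session arm. If enquiries are independent, P(at least one false AE) = 1 − (1 − q)^k:

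| q (assumed) | 5 sessions, k = 6 | 10 sessions, k = 11 | Odds ratio |
|---|---|---|---|
| 0.01 | 5.9% | 10.5% | 1.88 |
| 0.02 | 11.4% | 19.9% | 1.93 |
| 0.05 | 26.5% | 43.1% | 2.10 |
| 0.10 | 46.9% | 68.6% | 2.48 |

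Now let the error accrue with time covered instead. From first session to last visit is 4 + 12 = 16 weeks in the 5-session arm. In the 10-session arm, nine gaps of about 3.5 days make 4.5 weeks, and 4.5 + 12 = 16.5 weeks. Holding the 5-session arm at 26.5%, the 10-session arm becomes 1 − 0.735^(16.5/16) = 27.2%. The odds ratio is (0.272/0.728)/(0.265/0.735) = 1.04.

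At the same error rate in the 5-session arm, the choice of model alone moves the odds ratio from 1.04 to 2.10. Neither version covers the opposite error, worsening taken as pre-existing.

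**The case against.** A reader might infer that no baseline symptoms are recorded, so that existing post-concussion symptoms will be counted as acupuncture AEs or real worsening will be dismissed. The documents do not support that. Six of the eleven overlapping symptoms have a pre-treatment measure. Only events starting after the first session are recorded, and staff ask about events since the last visit. The principal investigator and study physician review every event (8.2), and causality is graded in five categories (8.3.3.2). Section 8.3.4 requires deterioration to be recorded. Eligibility excludes other serious neurological, psychiatric and chronic pain disorders (5.2). Section 9.4.3 plans no inferential statistics on these outcomes. Study forms outside the documents might hold more detail.

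Most of this stands, and it narrows the point. Three things remain:

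- Applying the start-date rule needs knowledge of whether the symptom was there before, which is what is missing for the five unmeasured symptoms.
- Causality grading does not protect an endpoint that counts any AE.
- The exclusion criteria concern serious disorders, not symptoms such as dizziness or tinnitus.

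The unequal number of enquiries is also a separate matter. It affects genuine events too, and a baseline form would not remove it.

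**Conclusion.** The gap is real but limited. The plan defines AEs against an earlier state, describes no medical-history or symptom record of that state, and does not tell assessors to use the measures it does collect. For dizziness, nausea, disturbed vision, tinnitus and imbalance the rule depends on recall. Section 9.4.5 also points to medical history in 8.1 that is not there, which needs correcting in any case.

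The Aim 2 endpoint is therefore open to misclassification in either direction. Its size cannot be derived: the documents give neither the prevalence of these symptoms at entry nor an error rate. The odds ratio of 2.1 should not be read as an estimate of bias; it rests on an assumed 5% error and on independent, equal-risk enquiries. The primary endpoint is not affected. This is a cheap improvement worth making, since a participant's pre-treatment state cannot be recorded afterwards.

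**What to change.** 1. Add one short REDCap form to the Schedule of Activities, completed before the first needle. It records current medical and psychiatric conditions and the presence and severity of the 2.2.1 symptoms, at minimum the five not otherwise measured.
2. State in 8.3.4 that AE assessors use this form, together with the baseline PSQI, TBI-QOL and diary, as the reference. Align the wording that now fixes baseline at screening, so that symptoms arising between screening and the first session have a place.
3. Keep the rule that any deterioration is recorded as an AE. A threshold of one severity grade is tempting, but on the three-level scale in 8.3.3.1 it would drop worsening within a grade that 8.3.4 now captures.
4. Reconcile 9.4.5 with 8.1: either list the medical-history variables and collect them, or remove the reference.
5. For participants already treated without the form, report AEs with and without symptoms that could have been pre-existing.

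Cost: about 5 minutes per participant and a minor amendment, with no extra visit or staff. The downside is that participants already treated will have no form. The amendment history shows treatment under way by May 2021, so the AE data would rest on two standards of baseline record and the report should say so.
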